### **Option 2: A 48-week cohort study with scheduled study visits**

Visit 1 (enrollment) will involve informed consent and participant characterization for the purpose of symptom cluster identification and receipt of systemic triamcinolone acetonide. Visit 2 will involve assessment of triamcinolone responsiveness. Visits 3, 4 and 5 are follow-up visits to assess the temporal stability of the symptom clusters. Visits 3, 4 and 5 can be completed in person or over the telephone.

This research is considered a clinical trial, because it involves an intervention (triamcinolone injection), and the study is designed to evaluate the efficacy of the intervention on symptoms and quality of life. The Emory Office of Clinical Research will facilitate the registration, periodic updates, and results reporting within ClinicalTrials.gov for the duration of the study.

## J. Outcome measures

Asthma exacerbations are an outcome of interest for all participants.

For participants enrolled in the 48-week cohort study, the primary outcome is corticosteroid treatment responsiveness, assessed 14 days after systemic triamcinolone administration (at visit 2). Responsiveness will be determined from the mean difference in the Asthma Control Questionnaire (**ACQ**) score between visit 1 (baseline) and visit 2 (14 days), with a reduction of 0.5 considered a minimally important difference.

The secondary outcome for participants enrolled in the 48-week cohort study is quality of life, assessed by the PROMIS Pediatric Asthma Impact Scale (**PAIS**) at visits 3, 4 and 5. As with all PROMIS measures, the PAIS is scored on the T-score metric, with higher scores reflecting more of the concept being measured. On the T-score metric, 50 is the mean of the reference population and 10 is the standard deviation; thus scores of 40 and 60 are one standard deviation lower and higher than the mean of the reference population, respectively.

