## **T. Sample size**

The sample size is 173 participants age 6 up to 21 years, which accounts for a conservative attrition rate of 15% (final N=147). The following assumptions were used for sample size calculations:

- Identification of 4 symptom clusters resulting in 3 degrees of freedom,

- >80% desired power for a chi-square test of multiple proportions,
- Two-tailed significance level of 0.05 if the effect size (W) is small-to-medium by Cohen's convention and equivalent to W=0.275 (small effect: W=0.10, corresponding odds ratio=1.49; medium effect: W=0.30, corresponding odds ratio=3.45), and
- Sample size allocation ratio of 1-2 per cluster group and sample sizes of at least 20 per group.

The sample size calculations with the above parameters should achieve at least 80% power as shown in **Table 3**.

For the secondary outcome, The sample size of 173 children necessary for the primary outcome should achieve >85% power to detect a difference of 0.2 between group means (considered a small effect size  $d$ ) with standard deviation of 0.20. Power >80% is achieved if the mean difference between groups and associated standard deviation is slightly larger but still small (0.25-0.30). In our prior study of triamcinolone administration to children with asthma, mean ( $\pm$  standard deviation) quality of life scores (on a different instrument, the Asthma Quality of Life Questionnaire) were 6.17 ( $\pm$  0.75) and 5.07 ( $\pm$  0.99), respectively. If similar differences are noted between two symptom cluster groups, we should have >90% power for the primary outcome and >95% for the secondary outcome if the groups have at least 20 participants. With smaller group sizes of only 13 participants, power would be >81% and >89% for the primary and secondary outcomes, respectively.

Drop-out	df	Power if effect size is:				
		0.250	0.275	0.300	0.325	0.350
10% (N=156)	3	0.749	0.833	0.897	0.941	0.969
	4	0.703	0.795	0.867	0.920	0.956
	5	0.664	0.760	0.840	0.900	0.942
12.5% (N=151)	3	0.734	0.820	0.886	0.933	0.963
	4	0.687	0.780	0.855	0.911	0.949
	5	0.648	0.744	0.826	0.889	0.934
15% (N=147)	3	0.721	0.808	0.877	0.926	0.959
	4	0.674	0.767	0.844	0.903	0.943
	5	0.634	0.731	0.814	0.878	0.927

**Table 3.** Estimated power.

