Because LTA is aimed at characterizing transition over time, it requires variability in all variables. Therefore, we will perform LTA with patient-reported symptoms (global, mental, social and physical health categories) and measures of asthma disease activity (ACQ, ACT, lung function, exhaled nitric oxide, blood eosinophils) measured at baseline and visits 3, 4 and 5 (**see Appendix 1**). Age, sex, race, ethnicity, socioeconomic status, medications, exposures and allergic sensitization measured at the baseline visit will be considered stable and treated as covariates in the LTA model. All participants will be included in the analysis since missing data for the variables are handled in the procedure, with data assumed to be missing completely at random. The test of the null hypothesis that data are missing completely at random (Missing Completely At Random test in the SAS LTA procedure) will be evaluated; if non-significant, missingness does not affect the interpretation of the results. The number of classes will be statistically determined using the Bayesian information criterion (**BIC**) and class prevalence if BICs are of a similar magnitude, to avoid a solution leading to low prevalent groups (<5%). To assess the stability of the group structure, goodness of fit of the “constrained” LTA model in which identical item-response probabilities across time are estimated (i.e., the same cluster structure is forced into multiple time points) will be compared with the “unconstrained” LTA model in which item response probabilities are estimated at each time point. To further address sex as a biological variable, models will also be fitted by sex, with statistical comparison of results observed in boys and girls. All analyses will be performed with SAS software version 9.4 (SAS Institute) using the PROC LTA procedure.

The primary outcome will be assessed after assignment of individuals to the latent classes that they had the highest probability of belonging to (based on the posterior probability provided by the model at baseline). A straightforward analysis of the primary outcome will follow and involves comparison of the proportion of children achieving a minimally importance difference in ACQ of at least 0.5 in each of the latent classes via a Chi-Square test.

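### Section J defines the primary outcome from a mean ACQ change, while Sections T and U size and test a 0.5-point responder proportion; state one variable, preferably the continuous change

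*Combined protocol and SAP*

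**What the plan says.** Section J (Outcome measures) gives the primary outcome for the 48-week cohort as corticosteroid responsiveness at 14 days: "Responsiveness will be determined from the mean difference in the Asthma Control Questionnaire" score between visit 1 and visit 2, "with a reduction of 0.5 considered a minimally important difference". It does not say whether 0.5 is a cut-off applied to each child or a yardstick for the mean.

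Section U (plan for aims 1-3) assigns each child to the most probable latent class at baseline. The primary analysis is then a "comparison of the proportion of children achieving a minimally importance difference in ACQ of at least 0.5 in each of the latent classes", by chi-square test and without covariates.

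Section T is built on the same test. It asks for ">80% desired power for a chi-square test of multiple proportions", assumes "Identification of 4 symptom clusters resulting in 3 degrees of freedom", and takes an effect "equivalent to W=0.275".

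Two further facts bear on this. Section U lists ACQ among the baseline measures that enter the latent transition model, and Section E enrols children whatever their level of asthma control. Baseline ACQ is not among the covariates listed in Section U.

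**The concern.** A mean change and a proportion crossing a threshold are different variables, with different tests and possibly different answers. Section J is where a reader looks for the definition of the primary outcome, and Section I says that results will be reported on a registry. As written, either version could be presented as the planned one.

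The choice has consequences. Cutting ACQ change at 0.5 discards information, so the version in Section U is the less powerful of the two. In addition, neither version takes account of visit-1 ACQ, although that score helps to form the classes being compared. Classes will probably differ in baseline ACQ, and a difference in response could then be regression to the mean or baseline severity rather than something particular to the symptom cluster.

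**Working it through.** **1. The plan's own figure.** Inputs from Section T: 173 enrolled with 15% attrition (173 × 0.85 = 147), 3 degrees of freedom, alpha 0.05, W = 0.275.

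- Noncentrality = N × W² = 147 × 0.275² = 11.12.
- Critical value of chi-square on 3 df = 7.815.
- Power = 0.808, as in Table 3. All 45 cells of Table 3 reproduce within 0.001.

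**2. The same effect on the continuous scale.** Assumptions, not in the documents: ACQ change is normal within class, with a common SD.

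*One class responds less, four equal classes.* Responder rates of 26.2% in one class and 57.9% in the other three average 50.0%.

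- W = √[(0.238² + 3 × 0.079²)/4 ÷ 0.25] ≈ 0.275.
- Normal quantiles are −0.637 and 0.199, a shift of 0.84 SD.
- Cohen's f = 0.837 × √(0.25 × 0.75) = 0.362.
- Noncentrality = 147 × 0.362² = 19.3; F critical value (3, 143 df) = 2.668; power = 0.966.

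*Equally spaced class means, four equal classes, 50% responders overall.* Rates of about 32, 44, 56 and 68% give W = 0.275 and f = 0.357.

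- Noncentrality = 147 × 0.357² = 18.7; power = 0.961.
- About 92 evaluable children would give the 0.808 that the chi-square test needs 147 for.
- The top-to-bottom class difference is 3 × 0.357/√1.25 = 0.96 SD, or 0.57 to 1.15 ACQ points if the SD lies between 0.6 and 1.2 (assumed).

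Over other class sizes, mean patterns and responder rates of 30 to 70%, f ran from 0.33 to 0.46 and power from 0.93 to 0.999.

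**3. Adding visit-1 ACQ as a covariate.** Let R² be the share of baseline ACQ variance explained by class and ρ the within-class correlation of baseline ACQ with improvement. The documents give neither. The class effect is assumed to lie along the baseline-ACQ gradient, with f = 0.357, N = 147 and 142 error df.

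- Adjusted effect held at f: noncentrality = N f² (1 − R²)/(1 − ρ²).
- Unadjusted difference held at f: noncentrality = N (±f − ρ√[R²/(1 − R²)])² (1 − R²)/(1 − ρ²), with plus if sicker classes improve more and minus if they improve less.

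| R² | ρ | Adjusted effect fixed | Unadjusted fixed, sicker improve more | Unadjusted fixed, sicker improve less |
|---|---|---|---|---|
| 0 | 0.5 | 0.992 | 0.992 | 0.992 |
| 0.2 | 0 | 0.909 | 0.909 | 0.909 |
| 0.2 | 0.5 | 0.971 | 0.172 | >0.99 |
| 0.4 | 0 | 0.801 | 0.801 | 0.801 |
| 0.4 | 0.5 | 0.909 | 0.068 | >0.99 |
| 0.6 | 0 | 0.609 | 0.609 | 0.609 |
| 0.6 | 0.5 | 0.748 | 0.438 | >0.99 |

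Adjusted power can therefore lie on either side of 0.808.

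**4. What the unadjusted test can pick up.** Simulation: four equal classes, N = 147, improvement dependent on baseline ACQ only, with no class effect of its own (assumed normal, mean improvement 0.5, SD 0.8; 4,000 runs).

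| R² | ρ | Chi-square rejects | Baseline-adjusted F test rejects |
|---|---|---|---|
| 0.2 | 0.3 | about 20% | about 5% |
| 0.2 | 0.5 | about 50% | about 5% |
| 0.4 | 0.3 | about 48% | about 5% |
| 0.4 | 0.5 | about 91% | about 5% |

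An unadjusted comparison of the continuous change has the same exposure, since the class means of change differ for the same reason. Moving to the continuous scale recovers power but does not cure this.

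**The case against.** The best defence is that there is no real ambiguity. Section J calls the outcome responsiveness and names the 0.5 threshold in the same sentence, so its reference to a mean difference may be loose wording for a responder definition. J names no test, while T and U name the same one. A responder proportion at the minimally important difference is interpretable, and Section T reaches its 80% target with it. Rewording one phrase in J would remove the conflict. This largely stands: a reader who inferred that the study has two rival primary analyses, or that the planned test misses its own target, would go further than the documents allow. What it leaves untouched is the power lost by dichotomising a score that is already collected.

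A second tempting reading is that ANCOVA on visit-1 ACQ should be the primary analysis and would bring power above 0.99. That figure comes from letting the covariate remove error variance while class is unrelated to baseline ACQ. Section U builds the classes partly from baseline ACQ, so the condition is unlikely to hold. The classes are not randomised either. Adjustment asks whether classes differ at equal baseline ACQ, which is not quite the Aim 2 question of whether the children with the poorest symptoms respond worst.

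In favour of adjustment, the low-power cases with the unadjusted difference fixed and ρ above zero need sicker classes to improve more, the opposite of the Aim 2 hypothesis. In the hypothesised direction those same cases give power above 0.99. Baseline dependence could also mask the predicted effect in the unadjusted test. That justifies reporting the adjusted comparison, but not requiring it as the primary one.

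**Conclusion.** The point holds as a modest inconsistency with a worthwhile improvement attached. Section J describes a mean change; Sections T and U use a responder proportion; the primary variable should be stated once. For an effect equivalent to W = 0.275 at N = 147, the continuous change without a covariate has power of about 0.96 to 0.97 against 0.81 for the chi-square test, and 0.93 to 0.999 over the scenarios tried. This rests on normal change and equal SDs, which the documents can neither confirm nor refute, since they give no SD, responder rate or baseline-change correlation.

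The gain comes from the continuous scale, not from the covariate. Baseline adjustment answers a different and useful question, and its power may be above or below 0.808. It belongs beside the unadjusted comparison, because the latter can reject on baseline severity alone.

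**What to change.** **Preferred.** In J, T and U, name the continuous ACQ change from visit 1 to visit 2 as the primary variable, compared across the latent classes by a one-way F test. Keep the proportion with a reduction of at least 0.5, and its chi-square test, as supportive.

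**Minimum.** Reword J as the per-child proportion with a reduction of at least 0.5, so that it matches T and U, and prespecify the continuous change as a supportive analysis.

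**In either case.** Prespecify a comparison adjusted for visit-1 ACQ as a sensitivity analysis. State that it compares classes at equal baseline ACQ and is there to show whether class differences merely reflect baseline severity or regression to the mean.

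**Cost.** No new data: Section K and Appendix I already schedule the ACQ at both visits. Under the preferred option, Section T needs a statement of the target effect on the continuous scale with its SD assumption, and Table 3 needs matching text. The headline result would be in ACQ points rather than percent responders.

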## **K. Visit-specific procedures**

Detailed procedures are listed below and also appear in the Appendix (Appendix I).

### **Option 1: A single study visit with telephone/email and electronic medical record follow-up for up to 48 weeks**

#### **Baseline visit (Visit 1), study week 0**

1. Informed consent obtained
2. Eligibility determined based upon inclusion and exclusion criteria
3. Brief physical examination (by RN) including height and weight performed
4. Medical history obtained
5. Urine pregnancy testing
6. Administer Demographic questionnaires
7. Asthma control evaluation (Asthma Control Questionnaire and Asthma Control Test)
8. Administer PROMIS symptom questionnaires
9. Measure exhaled nitric oxide
10. Perform spirometry with oscillometry (with bronchodilator reversibility)
11. Perform venipuncture for:
  - a. Total IgE (Children's Healthcare of Atlanta)
  - b. Inhalant allergen specific IgE (Children's Healthcare of Atlanta)
  - c. Complete blood count with differential (Children's Healthcare of Atlanta)
  - d. Plasma and white blood cells for aim 3 ([name] laboratory)
12. Perform sputum induction with samples stored for aim 3 ([name] laboratory)

#### **Telephone/email contact at 24 weeks and 48 weeks**

1. Medical history obtained
2. Asthma control evaluation (Asthma Control Questionnaire, Asthma Control Test, Pediatric Asthma Impact Questionnaire)

### **Option 2: A 48-week cohort study with scheduled study visits**

#### **Baseline visit (Visit 1), study week 0**

1. Informed consent obtained
2. Eligibility determined based upon inclusion and exclusion criteria
3. Brief physical examination (by RN) including height and weight performed
4. Medical history obtained

5. Urine pregnancy testing
6. Administer Demographic questionnaires
7. Asthma control evaluation (Asthma Control Questionnaire and Asthma Control Test)
8. Administer PROMIS symptom questionnaires
9. Measure exhaled nitric oxide
10. Perform spirometry with oscillometry (with bronchodilator reversibility)
11. Perform venipuncture for:
  - a. Total IgE (Children's Healthcare of Atlanta)
  - b. Inhalant allergen specific IgE (Children's Healthcare of Atlanta)
  - c. Complete blood count with differential (Children's Healthcare of Atlanta)
  - d. Plasma and white blood cells for aim 3 ([name] laboratory)
12. Perform sputum induction with samples stored for aim 3 ([name] laboratory)
13. Triamcinolone acetonide injection

**Steroid Responsiveness visit (Visit 2), Study Week 2 (window +7 days)**

1. Brief physical examination (by RN) including height and weight performed
2. Medical history obtained
3. Urine pregnancy testing
4. Asthma control evaluation (Asthma Control Questionnaire and Asthma Control Test)
5. Administer PROMIS symptom questionnaires
6. Measure exhaled nitric oxide
7. Perform spirometry with oscillometry (with bronchodilator reversibility)
8. Perform venipuncture for:
  - a. Complete blood count with differential (Children's Healthcare of Atlanta)
  - b. Plasma and white blood cells for aim 3 ([name] laboratory)
9. Perform sputum induction with samples stored for aim 3 ([name] laboratory)

**Follow-up visits (Visits 3 and 4), Study Week 16, 32 (window +4 weeks)**

1. Brief physical examination (by RN) including height and weight performed\*
2. Medical history obtained
3. Urine pregnancy testing\*
4. Asthma control evaluation (Asthma Control Questionnaire and Asthma Control Test)
5. Administer PROMIS symptom questionnaires
6. Measure exhaled nitric oxide\*
7. Perform spirometry with oscillometry\*

\*procedure will not be performed if follow-up occurs by telephone

**Final follow-up visit (Visit 5), Study Week 48 (window +4 weeks)**

1. Brief physical examination (by RN) including height and weight performed\*
2. Medical history obtained
3. Urine pregnancy testing\*
4. Asthma control evaluation (Asthma Control Questionnaire and Asthma Control Test)
5. Administer PROMIS symptom questionnaires

6. Measure exhaled nitric oxide\*
7. Perform spirometry with oscillometry (with bronchodilator reversibility)\*
8. Perform venipuncture:
  - a. Complete blood count with differential (Children's Healthcare of Atlanta)
  - b. Plasma and white blood cells for aim 3 ([name] laboratory)
9. Perform sputum induction with samples stored for aim 3 ([name] laboratory)\*

\*procedure will not be performed in follow-up occurs by telephone

## L. Procedural details

**Asthma control evaluation.** Asthma control and associated respiratory symptoms will also be assessed with the Asthma Control Questionnaire (**ACQ**) and the Asthma Control Test (**ACT**). The ACQ can be completed by children down to 6 years with strong measurement properties when administered by a trained interviewer. The ACQ is sensitive to short-term changes in asthma control and has well-documented reliability and cross-sectional and longitudinal validity in diverse asthma populations across a wide range of severities. This 7-item questionnaire includes questions related to daytime and nocturnal symptoms, short-acting bronchodilator use, and lung function during the clinic visit on that day. A higher score indicates poorer asthma control. The ACT can be completed directly by children 12 years and older; children 6-11 years will complete the Childhood ACT (**C-ACT**). Both tools have been extensively validated and have excellent measurement properties. For both tests, individual items about respiratory symptoms (5 and 7 in total for ACT and C-ACT, respectively) are summed; scores of 19 or less reflect uncontrolled asthma.

**PROMIS symptom questionnaires.** Symptoms will be assessed with validated PROMIS measures for children. PROMIS measures will be completed directly by children age 8-21 years, with caregiver assistance for children 6-7 years. The following PROMIS short-form measures will be utilized:

- Pediatric Life Satisfaction (4a)
- Pediatric Meaning and Purpose (4a)
- Pediatric Physical Stress Experience (4a)
- Pediatric Physical Activity (4a)
- Pediatric Positive Affect (4a)
- Pediatric Psychological Stress Experiences (4a)
- Pediatric Family Relationships (4a)
- Pediatric Asthma Impact (8a)
- Pediatric Anger (5a)
- Pediatric Anxiety (8a)
- Pediatric Depressive Symptoms (8a)
- Pediatric Fatigue (10a)
- Pediatric Peer Relationships (8a)

**Spirometry with Oscillometry.** Spirometry for measurement of lung function will be performed with a portable spirometer (MGC Diagnostics® CPFS/D USB™) according to technical standards. The best of three forced vital capacity maneuvers will be interpreted according to population reference standards. Oscillometry will be performed in cooperative participants (typically age 3 and older) with the TremoFlo C-100 device (Thorasys). Participants will wear a noseclip and take tidal breaths through a mouthpiece for 20 seconds. Airway resistance and reactance will be recorded.

**Bronchodilator reversibility testing.** Participants will receive 4 inhalations of albuterol from a metered dose inhaler (MDI) and valved holding chamber and spirometry will be repeated 15 minutes later.

**Exhaled nitric oxide.** Exhaled nitric oxide will be measured with a commercial device (NIOX VERO®, Circassia) using recommended standards. The procedure is non-invasive and considered to be an indirect measurement of airway inflammation. Participants will be instructed to take in a deep breath and blow air out at a constant pressure. One measurement will be taken and recorded.

**Venipuncture.** Blood will be collected by venipuncture as outlined in the table below. Participants will have the option to receive anesthetic cream prior to venipuncture.

Test	Where performed	Test code	Visits	Collection tube	Blood collection volume
Total IgE and Specific IgE	Children's	TIGE, INHALA Panel	1	Gold top SST	1.5 mL
Complete blood count with differential	Children's	CBED	1,2,5	Lavender EDTA	1 mL
Cytokines, metabolomics	[name] lab		1,2,5	Lavender EDTA Blue tempus	~6 mL ~3 mL (+6 mL solution)

**Table 2. Blood collection procedures**

**Urine collection for pregnancy testing.** Urine will be collected in females of child-bearing potential by clean-catch methods for the purpose of pregnancy testing. Unused urine will be discarded.

**Sputum induction.** Sputum induction will be performed in participants 12 years and older after pre-treatment with 4 inhalations of albuterol sulfate delivered through a MDI and holding chamber. 3% saline (substitutions permitted) will be inhaled through an ultrasonic nebulizer for a maximum of 12 minutes, with breaks every 2 minutes. To ensure safety, the procedure will only be performed on children with a post-bronchodilator FEV1 of >70% predicted; spontaneous sputum samples may be collected on children with an FEV1 below

these limits. A physician will be available during the challenge; study staff will calculate and record the FEV1 value that equals both a 10% and 20% fall in lung function based upon the recorded post-bronchodilator FEV1 values. Participants will not be discharged until their FEV1 is within 10% of their post bronchodilator FEV1 and will be given albuterol sulfate (2 inhalations as needed) for this purpose. Sputum samples will be processed by the [name] laboratory.

**Triamcinolone acetonide injection.** Each participant who meets inclusion/exclusion criteria will receive triamcinolone acetonide intramuscularly at the end of visit 1. Children 6-21 years will receive 1 mg/kg triamcinolone acetonide (up to 40 mg maximum).

Triamcinolone acetonide will be administered as a single intramuscular dose deep in the gluteal region.

